5.8 PROHIBITED CONCOMITANT MEDICATION

Use of the following concomitant medications is prohibited within 72 hours of the baseline EEG (Day 0), but are otherwise allowable in the study:

- Anti-Migraine
- Benzodiazepines and Partial Benzodiazepine Agonists (see section 5.7 for clarification)
- Non-Benzodiazepine Hypnotics
- Non Sedating Antihistamines
- Cough Suppressants (Dextromethorphan, etc)

Uses of the following concomitant medications are excluded throughout the study and should be washed out at least 1 week prior to baseline (Day 0):

- Anticholinergics
- Anticonvulsants
- Antidepressants (note: fluoxetine shall be washed out 4 weeks prior to baseline)
- Antihistamines (with sedating effects)
- Anti-Parkinsonian medications
- Antipsychotics
- Barbiturates
- Codeine or Oxycodone containing compounds
- Corticosteroids (tablet forms only)
- Cold Pills (with sedating ingredients)
- Medications that are known to reduce seizure thresholds:
 - a. Accurbron/Accubron
 - b. Doxepin
 - c. Ambenonium Chloride
 - d. Amitriptyline
 - e. Imipramine
 - f. Amoxapine
 - g. Trazodone
 - h. Amphetamine sulfate
 - i. Baclofen
 - j. Chlorpromazine
 - k. Clozaril
 - l. Cocaine
 - m. Lithium
 - n. Protostat
- Mood stabilizers
- Muscle relaxants
- Other sleep aid medications with anticholinergic properties (prescription OR over-the-counter)
- Opioid analgesics

- Pseudoephedrine combination forms that contain excluded medication (pseudoephedrine (e.g. Sudafed) in pure form is acceptable during the study)
- Psychostimulants

The following Nutritional supplements are excluded throughout the study and should be washed out at least 1 week prior to baseline (Day 0):

- CQ-10
- Ginkgo Biloba
- Ginseng containing supplements
- Sam-E
- St John's Wort
- High doses of Omega-3 fatty acids and fish oil supplements (note: this is acceptable if subject is taking ≤ 1000 mg QD or reported taking the supplements for at least one month prior to starting the study).

Caffeinated Beverages (e.g. Energy Drinks, Coffee, Cola Products): The subject should not deviate from their normal consumption patterns. EEG should not be collected within one hour of consumption of any caffeinated beverage.

Alcoholic Beverages: Subjects should refrain from overconsumption of alcoholic beverages on the night preceding and the day of their EEG visits.

[figure not shown]

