- Vital Signs (Heart Rate [HR], Blood Pressures [BP])
- Weight
- Pregnancy Test (HCG)
- Urine Toxicology Screen
- HAM-D/MADRS (Montgomery-Åsberg Depression Rating Scale)
- IDS-SR (Inventory of Depressive Symptomatology – Self Report)
- C-SSRS (Columbia Suicide Severity Rating Scale)
- Standard 12 lead ECG (optional)
- Physical Examination (optional)
- Laboratory Assessments (optional)

FOLLOW-UP VISITS

General Overview: The first treatment (Day 1) may occur on the same day as the baseline visit (Day 0) if all study criteria are met and randomization procedures are complete, or subjects will be asked to return on a subsequent day to begin the weekly treatment schedule. Subjects will come to the clinic for 5 daily treatment sessions per treatment week for a total of 30 treatment sessions over 6 treatment weeks. A consistent Monday through Friday weekly treatment schedule will be highly encouraged. However, a visit interval of 5-10 calendar days will be allowed for each treatment week to accommodate visit scheduling adjustments when needed. Treatment will be discontinued at the end of Week 6 (30 treatment sessions). Subjects will be clinically evaluated for safety and efficacy at the end of each of the six weekly treatment

courses. Subjects who have not remitted (remission defined as a HAM-D¹⁷ score of ≤ 7 (Zimmerman et al., 2004)) at the Week 6 evaluation visit may be eligible to receive open label sTMS during the six-week follow-up phase. If so, additional weekly treatment evaluation visits shall be performed at the end of treatment Week 7, 8, 9, 10, 11 and 12. Subjects who do not meet response criterion (relative to pretreatment baseline, Day 0) following 3 weeks (15 treatments) of open label treatment may be offered additional concomitant antidepressant therapy for the final 3 weeks of open label treatment.

Alternatively, if the clinician feels it is not appropriate for the subject to participate in the open label sTMS follow-up, the subject chooses not to participate in the open label follow-up or if the subject has remitted in the blinded phase, subject will be deemed to have completed participation in this study.

Specifics of the study visits are as follows:

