The Per-Protocol (PP) study sample is comprised of randomized subjects who receive the correct randomized treatments according to the protocol schedules without any major protocol violation. This is the primary analysis population per e-mail discussion between NeoSync and the Food and Drug Administration (FDA) on July 17, 2015. Major protocol violations include but are not limited to:

- Receiving treatments other than the randomized treatments.
- Treatments not administered according to study protocol.
- Subjects cannot miss more than 1 dose in a treatment week and their weekly visit interval cannot exceed 10 calendar days. Any subject who misses more than 6 doses in the 6 week treatment period is not considered compliant with the treatment and will not be included in the PP analysis population.
- Receiving concomitant medications that are not allowed per the study protocol; the prohibited medications are as follows:

Use of the following concomitant medications is prohibited within 72 hours of the baseline EEG (Day 0), but is otherwise allowable in the study:

- Anti-Migraine

- Benzodiazepines and Partial Benzodiazepine Agonists
- Non-Benzodiazepine Hypnotics
- Non-Sedating Antihistamines
- Cough Suppressants (Dextromethorphan, etc.)

Uses of the following concomitant medications are excluded throughout the study and should be washed out at least 1 week prior to baseline (Day 0):

- Anticholinergics
- Anticonvulsants
- Antidepressants (note: fluoxetine shall be washed out 4 weeks prior to baseline)
- Antihistamines (with sedating effects)
- Anti-Parkinsonian medications
- Antipsychotics
- Barbiturates
- Codeine or Oxycodone containing compounds
- Corticosteroids (tablet forms only)
- Cold Pills (with sedating ingredients)
- Medications that are known to reduce seizure thresholds:
 - a. Accurbron/Accubron
 - b. Doxepin
 - c. Ambenonium Chloride
 - d. Amitriptyline
 - e. Imipramine
 - f. Amoxapine
 - g. Trazodone
 - h. Amphetamine sulfate
 - i. Baclofen
 - j. Chlorpromazine
 - k. Clozaril
 - l. Cocaine
 - m. Lithium
 - n. Protostat
- Mood stabilizers
- Muscle relaxants
- Other sleep aid medications with anticholinergic properties (prescription OR over-the-counter)
- Opioid analgesics
- Pseudoephedrine combination forms that contain excluded medication (pseudoephedrine (e.g., Sudafed) in pure form is acceptable during the study)
- Psychostimulants

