For the six-week double-blind phase, imputation of data on the primary endpoint will be performed as described below. For the six-week follow-up open-label phase (Weeks 6 – 12), all efficacy and safety summaries will be based on the all sTMS treated subject population, which consists of all subjects who have entered the six-week follow-up Phase. All efficacy analyses will be performed on the Observed Cases (OC) dataset only for each week in this open-label Phase. That is, no imputation will be used, and only data observed during the follow-up Phase will be summarized. Analyses in the open-label phase will be presented by double-blind

treatment group and for both treatment groups combined. Baseline for the double-blind phase will be defined as the last available value measured post-washout and prior to the first double-blind dosing. Baseline for the open-label phase will be defined as (a) the last post-washout assessment measured prior to the beginning of the double-blind treatment phase for patients randomized to sTMS in the double-blind phase; and (b) the last double-blind assessment measured prior to the beginning of the open-label phase for patients randomized to Sham in the double-blind phase.

Analysis of Primary Efficacy Endpoint

HAM-D/MDRS will be assessed at screening, baseline, Week 1-6 Evaluation Visits, and during the open-label phase through Week 12 evaluation visit. The primary efficacy endpoint is clinical response, defined by 50% or greater reduction on the HAM-D¹⁷ from baseline to Week 6. The efficacy analyses will be performed on the PP, ITT with available data, and ITT with imputed data (see below for imputation methods) analysis populations. The PP analysis population is the primary analysis population for efficacy per e-mail discussion between NeoSync and the FDA on July 17, 2015.

The null hypothesis is that the active sTMS treatment group does not differ from the sham group with respect to the proportion of patients with clinical response at Week 6. The corresponding alternative hypothesis is that the active sTMS treatment group differs from the sham group with respect to the proportion of patients with clinical response at Week 6.

Specifically, the primary efficacy analysis will be a test of the hypotheses:

$$H_0: \pi_A - \pi_S = 0$$

and

$$H_a: \pi_A - \pi_S \neq 0$$

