where π_A is the proportion of subjects who show 50% or greater improvement in mean HAM-D¹⁷ total score from baseline (Day 0) to Week 6 for the active treatment and π_S is the equivalent value for the sham-controlled group. The test of the null hypothesis will be based on Fisher's exact test at a two-sided 0.05 level of significance. In addition, the observed response rates and two-sided 95% confidence intervals of the risk difference between treatments will be presented, calculated using the Wilson method discussed in Newcombe (1998).

An assessment of treatment-by-investigative center interaction on the proportion of clinical responders at Week 6 will be carried out using the Breslow-Day test. Sites with fewer than 10 subjects in the PP group will be pooled with other centers by geographic region prior to carrying out analyses (the same pooled sites will then be used for the analyses on the ITT analysis population). The pooling will be carried out before the blind is broken. A 0.15 level of significance will be used to assess the interaction. A non-significant interaction or an interaction significant but only quantitative in nature will support the pooling of results across study centers for the final analysis.

For the six-week open-label follow-up phase, the proportion of patients with a clinical response at each open-label visit for each double-blind treatment and for both treatments combined will be presented. The proportion of patients with a clinical response at each visit will be compared between double-blind treatment in a similar manner as above. These open-label analyses are

considered exploratory.

INTERIM ANALYSES

Due to uncertainty regarding the expected sham response rate and resulting treatment effect differential, this study will utilize an adaptive design that allows one interim sample size re-estimation after a minimum of 70 subjects have been enrolled and completed 6 weeks of treatment (or dropped out prior to 6 weeks). The pre-specified maximum allowable adjusted sample size following re-estimation will be 240 randomized, or two times the initial planned sample size of 120 enrolled, based on practical resource constraints and the desire to achieve a minimum differential of 12% between active and sham response rates. The re-estimation of sample size will be conducted by an independent biostatistician following a pre-specified plan as described by Mehta and Pocock, 2010 and presented to the independent data monitoring board (DMB).

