For the six-week follow-up open-label phase, double-blind treatments will be compared on the above endpoints at Week 12 in a similar manner as described above. Here, baseline will be defined as the last post-washout assessment measured prior to the beginning of the double-blind treatment phase for patients randomized to sTMS in the double-blind phase; baseline will be defined as the last double-blind assessment measured prior to the beginning of the open-label phase for patients randomized to Sham in the double-blind phase. There will be no assessment of interactions with investigative site, nor will there be imputation of missing data.

I. Exploratory Analyses

Exploratory efficacy variables are listed below. Analyses comparing treatments on these variables will be carried out on the ITT and PP populations; there will be no imputation of missing data, and there will be no assessment of center-by-treatment interactions.

- Change from baseline in HAM-D¹⁷ score at each time point;
- Change from baseline in MADRS score at each time point;
- Remission at each visit, where remission is defined by a total score of ≤ 10 on the MADRS;
- Change from Baseline on the HAM-D¹⁷ subscale scores (Maier, anxiety, retardation and sleep) at each time point;

- Change from Baseline on the HAM-D²⁴ and HAM-D²⁸ at each time point;
- Clinical response (as defined above for HAM-D¹⁷) for HAM-D²⁴ and HAM-D²⁸ at each time point;
- Change from Baseline on the IDS-SR30 scale at each time point.

Change from Baseline on the HAM-D¹⁷, HAM-D²⁴ and HAM-D²⁸ scores, IDS-SR30 score, and MADRS score will be analyzed using analysis of covariance at each visit adjusting for the baseline value of the endpoint. Proportion of subjects with remission and with clinical response will be analyzed using Fisher's Exact test at each visit.

J. Safety Analysis

The assessment of safety will be based mainly on the frequency of adverse events recorded. Other safety data (e.g., vital signs and ECG) will not be collected systematically but will be considered as appropriate. All safety analyses will be performed on the Safety Population as defined above. Safety summaries will be performed for each of the active and Sham treatments.

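### Antidepressants are excluded for the whole study in one place and allowed in open-label Weeks 10-12 in another, and the SAP's Week 12 comparison of three endpoints has no rule for add-on use

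*SAP*

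**What the plan says.** **Exclusion.** Protocol 5.8 states: "Uses of the following concomitant medications are excluded throughout the study". Antidepressants are on the list that follows. The SAP repeats the list in its Per Protocol definition (Statistical Cohorts), with the entry "Antidepressants (note: fluoxetine shall be washed out 4 weeks prior to baseline". There, receiving a disallowed medication is a major protocol violation. Neither list makes an exception for the open-label phase.

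**Allowance.** Protocol 7.1 and the SAP's Follow-up Visits overview carry the same provision. It applies to "Subjects who do not meet response criterion (relative to pretreatment baseline, Day 0) following 3 weeks (15 treatments) of open label treatment", who "may be offered additional concomitant antidepressant therapy for the final 3 weeks of open label treatment".

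**Open-label analysis.**
- SAP section H, after the secondary endpoints (HAM-D17 change, MADRS change, MADRS response), states for the open-label phase: "double-blind treatments will be compared on the above endpoints at Week 12 in a similar manner as described above".
- For HAM-D17 response, the SAP's primary endpoint section states: "The proportion of patients with a clinical response at each visit will be compared between double-blind treatment in a similar manner as above". It calls these open-label analyses "considered exploratory".
- On data handling in the open-label phase, the SAP's general overview of methods states: "no imputation will be used, and only data observed during the follow-up Phase will be summarized".

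**The concern.** There are two linked problems.

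First, the documents give incompatible instructions. A site that follows Protocol 7.1 in Weeks 10-12 is using a drug class that Protocol 5.8 excludes without exception. Because the SAP places the exclusion inside the Per Protocol definition, and that population is primary for efficacy, the conflict also leaves open whether open-label medication can change who is counted in the Week 6 primary analysis.

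Second, the add-on is offered only to subjects who are doing poorly, and three endpoints are compared between the former arms at the last visit of the add-on window. With no rule for scores after add-on start, the Week 12 result describes sTMS plus selective drug use, and the amount of drug use may differ between the former arms.

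**Working it through.** The plan states no figure on this point, so there is none to reproduce. The check sets the passages side by side; the arithmetic on size is illustrative.

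**1. Timing.** There are 5 treatments per treatment week, and open-label treatment starts in Week 7. Fifteen treatments take 15 / 5 = 3 weeks (Weeks 7, 8 and 9). Protocol 7.3 places the open-label evaluation on the last day of each weekly cycle, so the Week 9 score is the last one before add-on is possible. Weeks 10, 11 and 12 form the add-on window, and Week 12 is its final visit.

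**2. Which comparisons fall in the window.**

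| Endpoint | Open-label comparison in the SAP | Visit before the window? |
|---|---|---|
| HAM-D17 response | each open-label visit, exploratory | yes, Weeks 7-9 |
| HAM-D17 change (section H) | Week 12 | no |
| MADRS change (section H) | Week 12 | no |
| MADRS response (section H) | Week 12 | no |

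**3. Handling of add-on use.** Nothing in the open-label efficacy text censors, flags, stratifies by or adjusts for add-on use, and nothing declares that scores count regardless of it. Use appears only in listings (section K) and in a descriptive count of psychotropic medication by group (section L).

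**4. Effect on the Per Protocol population.** The double-blind analysis is run once all randomized subjects have finished Week 6 or withdrawn. Early enrollees may by then have Week 10-12 medication records. The SAP finalises major violations before unblinding but does not limit the medication violation to Weeks 1-6. Read literally, it could remove subjects who were non-remitters at Week 6 and non-responders at Week 9, which would be a selective loss.

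**5. Size, with assumed inputs.** The documents give no open-label response rate, add-on uptake or drug effect.
- Share eligible for add-on = 1 - (Week 9 response rate).
- Rise in a group's Week 12 response = (Week 9 non-response) x (uptake) x (added response on drug). With non-response 50% to 90%, uptake 25% to 100% and added response 10 to 30 points, the range is 0.50 x 0.25 x 0.10 = 0.0125 to 0.90 x 1.00 x 0.30 = 0.27, or about 1 to 27 points.
- Shift in the between-arm difference, if Week 9 non-response differs by 20 points and uptake and drug effect are equal: 0.20 x 0.25 x 0.10 = 0.005 to 0.20 x 1.00 x 0.30 = 0.06, or 0.5 to 6 points.

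The ranges are wide because every input is assumed. They show direction and order of size only.

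**The case against.** The strongest case on the other side has five parts.

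- **Status.** The primary endpoint and the gated secondary tests are all at Week 6, before open-label treatment begins. A reader might infer that add-on drugs distort those results. The documents do not support that: no Week 6 score can contain an add-on effect. Only the question of Per Protocol membership remains open, and limiting the violation to Weeks 1-6 was probably intended.
- **Coverage.** A reader might infer that Week 12 is the only open-label comparison. It is not: HAM-D17 response is compared at every open-label visit. Section I also analyses HAM-D17 and MADRS change at each time point, without saying whether open-label visits count. Neither places MADRS response at Week 9 or gives Week 9 a defined role. The exploratory label is attached to the response analyses and is not repeated for the Week 12 comparison in section H.
- **No device contrast to distort.** Both former arms receive active sTMS in the open-label phase, and the baseline differs by former arm (pre-treatment for sTMS, last double-blind assessment for sham). The comparison could not isolate a device effect even without add-on drugs. This stands, and it limits the point to how the Week 12 summaries and comparison are read.
- **Uptake.** A reader might infer that most open-label subjects would be on an antidepressant by Week 12, for instance 60% to 80% if Week 9 response were 20% to 40%. That needs every eligible subject to accept, whereas the offer is optional. Those response rates are also assumed, and the open-label group includes Week 6 responders who had not remitted.
- **Legitimate reading.** Observed scores can be taken as the outcome under sTMS plus permitted add-on. That is defensible, but the SAP does not declare it, and the exclusion lists contradict it.

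**Conclusion.** The concern holds in limited form. The exclusion and the allowance contradict each other in both documents. The SAP ties three open-label endpoints to the end of the add-on window without saying how add-on use is handled. Week 12 results for those endpoints will mix sTMS with outcome-triggered drug use, possibly unequally between the former arms.

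The size cannot be determined from the documents. The eligible share, 1 minus the Week 9 response rate, bounds add-on use from above. The illustrative shifts in response (about 1 to 27 points within a group, 0.5 to 6 points between groups) rest wholly on assumed inputs.

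The matter concerns the open-label phase, with one link to the primary analysis: whether open-label medication can affect Per Protocol membership. It is a cheap improvement and not a threat to the Week 6 result.

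**What to change.** 1. Reconcile Protocol 5.8 and the SAP's Per Protocol medication list with Protocol 7.1 and the SAP's Follow-up Visits section. Which clinical rule stands is for the sponsor and investigators to settle.
2. State in the SAP, before unblinding, whether medication taken in the open-label phase can affect membership of the Per Protocol population for the Week 6 analysis.
3. Make Week 9 the main open-label time point for HAM-D17 change, MADRS change and MADRS response.
4. If the add-on provision is kept, retain Week 12 and describe it as the outcome under sTMS plus permitted add-on. Show Week 12 results by add-on use, as description only because the split follows outcome. Add a sensitivity analysis of response that counts add-on users as non-responders.
5. Do not simply drop scores after add-on start. Add-on goes only to Week 9 non-responders, so what remains is enriched for responders. For example, with 30% response at Week 9 and full uptake (both assumed), only that 30% would be left at Week 12.

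**Cost.** SAP wording, a protocol clarification and a little extra programming. HAM-D and MADRS are already scheduled weekly through Week 12, and medication start and stop dates are already recorded (Protocol 5.7 and Appendix I), so no new data are needed. The downside is that the main open-label comparison covers 3 weeks of treatment rather than 6.

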11 STATISTICAL METHODS

11.1 POPULATION FOR ANALYSIS

The Intent-to-Treat (ITT) Population will consist of all subjects who are randomized to a study group.

The Per-Protocol (PP) Population is comprised of subjects who receive treatments according to the recommended protocol schedule without any major protocol violation. Major protocol violations include but are not limited to:

- Receiving treatments other than those specified in the study protocol.
- Treatments not administered according to study protocol.
 - Subjects cannot miss more than 1 dose in a treatment week and their weekly visit interval cannot exceed 10 calendar days. Any subject who misses more than 6 doses in the 6 week treatment period (maximum of 60 days) is not considered compliant with the treatment and will not be included in the analysis.
- Receiving concomitant medications that are not allowed per the study protocol.
- HAM-D₁₇ not available at Week 6.

The PP population analysis will serve as the primary analysis population.

The Safety Population will consist of all subjects who received at least one study treatment.

For the six-week open label phase, all efficacy and safety summaries will be based on the combined sTMS-treated subject population, which consists of all subjects who have entered the six-week open label phase. For the open-label phase, all efficacy analyses will be performed on the Observed Cases (OC) dataset only. That is, no imputation for missing data will be used, and only data observed during the follow-up phase will be summarized.

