The following Nutritional supplements are excluded throughout the study and should be washed out at least 1 week prior to baseline (Day 0):

- CQ-10

- Ginkgo Biloba
- Ginseng containing supplements
- Sam-E
- St John's Wort
- High doses of Omega-3 fatty acids and fish oil supplements (note: this is acceptable if subject is taking $\leq 1000\text{mg}$ QD or reported taking the supplements for at least one month prior to starting the study).
- HAM-D17 not available at Week 6.

The final major protocol violations will be reviewed and defined prior to unblinding the treatment randomization.

STATISTICAL ANALYSES

General Overview of Methods

This is a randomized, double-blinded, sham-controlled, parallel group study to evaluate the effectiveness of sTMS in subjects with Major Depressive Disorder (MDD). The objective of this study is to establish the efficacy of sTMS in comparison to sham treatment in subjects with major depressive disorder.

The primary endpoint is clinical response, defined by 50% or greater reduction on the HAM-D17 total symptom scores following 6 weeks of double-blind treatment (Week6).

The data analysis on the double-blind portion will be performed when all randomized subjects have completed the double-blind Week 6 visit or have withdrawn from the study prior to completion of the double-blind phase. The data analysis on the open-label portion will be performed when all open-label subjects have completed the Week 12 visit or have withdrawn from the study prior to the open-label Week 12 visit.

The standard descriptive statistics such as mean, standard deviation, median, quartiles, minimum, and maximum will be used to summarize the continuous variables. For discrete variables, the frequency and percentage of patients in each category will be calculated.

Sites with fewer than 10 subjects in the PP group will be pooled with other centers by geographic region prior to carrying out analyses described below. All statistical tests will be two-sided with a significant level of 0.05. All confidence intervals will be two-sided with a confidence level of 95%. Statistical analyses will be conducted with SAS Version 9.4 or larger.

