Specifically, at the interim stage the conditional power (CP) for obtaining a significant beneficial effect of sTMS over sham with respect to the primary endpoint will be calculated by the independent statistician, using the protocol-specified planned sample size of 92 *evaluable* patients. This conditional power will be calculated using formula (6) in Mehta and Pocock (2010) under the assumption that the interim estimate of the risk difference is the true population risk difference. The study will not be stopped for overwhelming efficacy or futility at this interim stage. Based on Table 1 of Mehta and Pocock (2010), if the $CP \leq 36\%$ or $CP \geq 90\%$, the study will continue to its original planned sample size of 92 evaluable subjects (120 enrolled subjects). Otherwise if $36\% < CP < 90\%$ (the Mehta and Pocock “promising zone”), then the sample size may be increased up to 240 enrolled subjects (~184 evaluable patients) in order to obtain enough evaluable subjects to yield up to 90% CP for the primary analysis (if the maximum increase to 240 enrolled patients does not yield 90% CP, the sample size may still be increased to 240 to maximize CP, at the recommendation of the independent DMB). This approach to sample size increase does not inflate the overall Type I error.

The sponsor and investigators will remain blinded to the interim results for the duration of the ongoing study. After the interim analysis is carried out, the recommendation made by the DMB to the sponsor will only be to keep sample size as is or to increase enrolled sample size to a given value; the reason for the recommendation will not be given to the sponsor.

OTHER STUDY PARAMETERS AND ANALYSES

The following will be carried out for the ITT and PP analysis populations unless otherwise specified.

A. Subject Disposition

The number and percentage of subjects in each population will be presented by treatment group. The number and percentage of subjects in each of the ITT and PP populations who prematurely discontinued prior to Week 6 will be presented overall and by reason of discontinuation within each treatment group. The number and percentage of ITT and PP subjects will be presented by investigative center within each treatment group.

The number and percentage of ITT and PP subjects entering the open-label phase will be presented overall and by original double-blind treatment group.

B. Baseline Demographics

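### The per-protocol medication and supplement exclusions have no cut-off at Week 6, so a listed item taken in the open-label phase can remove a subject from the primary Week 6 analysis

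*SAP*

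**What the plan says.** The SAP (Analysis of Primary Efficacy Endpoint) states that "The PP analysis population is the primary analysis population for efficacy". The endpoint is HAM-D17 response at Week 6, the end of the double-blind phase.

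Under Statistical Cohorts, Per Protocol, the SAP counts disallowed concomitant medication as a major violation and places the prohibited list inside the definition: "Uses of the following concomitant medications are excluded throughout the study". For supplements it says "The following Nutritional supplements are excluded throughout the study". A further criterion is "Receiving treatments other than the randomized treatments", where Protocol 11.1 has "Receiving treatments other than those specified in the study protocol". None of these has an end date. By contrast, the total missed-dose limit refers to the 6-week treatment period, the first drug list to the 72 hours around the baseline EEG, and the availability criterion to the Week 6 HAM-D17.

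The study goes on after Week 6 for some subjects. Non-remitters may enter six weeks of open-label sTMS (SAP, Follow-up Visits), and medications are collected through Week 12 (SAP, K. Other Assessments). For the others, "if the subject has remitted in the blinded phase, subject will be deemed to have completed participation in this study". On timing: "The data analysis on the double-blind portion will be performed when all randomized subjects have completed the double-blind Week 6 visit" or have withdrawn. Major violations are finalised before unblinding, with no data cut-off given.

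**The concern.** Membership of the primary analysis set should depend on nothing that happens after the endpoint is measured. As worded, a muscle relaxant, codeine compound or listed supplement taken in open-label Week 9 is use during the study, and so a major violation for a subject whose Week 6 score is already on file.

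The exposure is not random. Only subjects with HAM-D17 above 7 at Week 6 can enter the open-label phase. With a baseline score of at least 17, a score of 7 or less is a reduction of at least 10/17 = 58.8%, so every remitter is a responder. Later events can therefore remove non-responders and non-remitting responders, but never a remitter. Exposure also depends on calendar time: when the last subject reaches Week 6, early enrollees may have a full open-label record and the last enrollees none. What is at stake is an avoidable loss of evaluable subjects and a primary set whose membership depends in part on outcome.

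**Working it through.** **1. The plan's own figure.** Inputs (SAP, Sample Size; Protocol 11.4): 46 per arm, 34% vs 8%, Fisher's exact test, two-sided 0.05, stated power 81%.
- Continuity-corrected formula: n = (m/4)·[1 + √(1 + 4/(m·d))]², with d = 0.26. For n = 46, m = 38.6, and the two-proportion power at m is 81.4%. This reproduces the stated 81%.
- Exact enumeration of Fisher's test gives 83.6%. This is the baseline below.

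**2. Number exposed.** In the earlier NEST study, 89 of 120 PP subjects entered the open-label phase (Protocol 1.1). Applied here: 92 × 89/120 = 68. This is an upper-end figure, because late enrollees have no open-label record when the double-blind analysis is run. Half of it, 34, is used as a second assumption.

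**3. Who is removed.** Remission rates in the non-naive NEST PP subgroup were 13.2% and 5.6% (Protocol 1.1).
- Expected non-remitters: 46 × 0.868 = 39.9 (sTMS) and 46 × 0.944 = 43.4 (sham).
- Splitting 68 entrants in that proportion gives 32.6 and 35.4.
- Response rate among non-remitters: (0.34 − 0.132)/0.868 = 24.0% and (0.08 − 0.056)/0.944 = 2.5%.

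**4. Use rate.** The documents give none. Assumed: 10%, 20% or 30% of entrants, equal in both arms. At 20% and 68 entrants:
- Removed: 6.5 and 7.1, leaving 39.5 and 38.9.
- Responders left: 46 × 0.34 − 6.5 × 0.240 = 14.1, and 46 × 0.08 − 7.1 × 0.025 = 3.5.
- Rates: 35.7% and 9.0%.

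**5. Results** (arm sizes rounded to whole subjects, exact Fisher power):

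| Entrants | Use | PP n, sTMS/sham | Response rates | Difference (points) | Power |
|---|---|---|---|---|---|
| none removed | – | 46/46 | 34.0% vs 8.0% | 26.0 | 83.6% |
| 68 | 10% | 43/42 | 34.8% vs 8.5% | 26.3 | 81.4% |
| 68 | 20% | 39/39 | 35.7% vs 9.0% | 26.7 | 77.1% |
| 68 | 30% | 36/35 | 36.7% vs 9.6% | 27.1 | 73.8% |
| 34 | 10% | 44/44 | 34.4% vs 8.2% | 26.2 | 81.3% |
| 34 | 20% | 43/42 | 34.8% vs 8.5% | 26.3 | 81.4% |
| 34 | 30% | 41/41 | 35.2% vs 8.7% | 26.5 | 79.8% |

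Simulation with every non-remitter exposed gives a similar range: 82%, 78% and 73% power at 10%, 20% and 30% removal.

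**6. Type I error.** With a true response rate of 15% in both arms and equal removal of non-remitters, simulated two-sided error was 2.5% with no removal and 2.9% to 3.4% with 25% to 74% removed, below the nominal 5% throughout.

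**The case against.** The strongest reply is that the plan, read as a whole, settles PP status by Week 6. The 23% allowance for non-PP subjects covers drop-out and noncompliance before Week 6 (SAP, Sample Size; likewise Protocol 11.4). The 92 evaluable subjects are those who complete the primary study phase, which ends at Week 6. The interim re-estimation presupposes that evaluability is known once subjects have finished or left the six weeks. The SAP also plans a table under which "The number and percentage of ITT and PP subjects entering the open-label phase will be presented overall and by original double-blind treatment group", which assumes that PP status survives open-label entry. All of this stands as evidence of intent. None of it is an operative rule, and it does not override an explicit exclusion that runs throughout the study.

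The ITT analyses are untouched, and violations are finalised before unblinding. Both mitigate. But that review hides the arm, not the Week 6 outcome, so dependence on outcome remains.

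Two stronger readings are tempting, and the documents do not support them. First, a reader might infer from "Receiving treatments other than the randomized treatments" that every former sham subject who takes open-label sTMS leaves the PP set. The bullet elaborates a sentence about receiving the correct randomized treatment, the Protocol 11.1 wording would not catch a treatment that the protocol itself specifies, the planned table assumes the opposite, and a review carried out before unblinding could not single out sham subjects. This is an unintended wording conflict to align. Second, a reader might infer a raised false-positive rate. That appears only if non-responders are removed more often from the active arm. With 50% vs 20% removed, the simulated chance of a false result favouring sTMS is about 10%, against 1.4% with no removal under a 15% rate in both arms. Nothing in the documents gives a reason to expect such an imbalance.

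**Conclusion.** The point holds as a defect of wording with a real but moderate effect. Followed literally, the medication and supplement criteria let events after the endpoint remove non-remitters from the primary Week 6 analysis.

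The cost is lost evaluable subjects: 92 falls to between about 85 and 71, and exact power from 83.6% to between about 81% and 74%, for 10% to 30% use among 68 entrants. With half that exposure, power stays at about 80% to 81%, close to the planned 81%. Response rates rise slightly in both arms and the difference hardly changes.

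These figures rest on an assumed use rate, on NEST uptake from a PP set that included treatment-naive subjects and had a four-week open-label phase, and on equal removal in both arms. A sensible team might apply a Week 6 cut-off anyway, but the plan should say so.

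**What to change.** In the SAP's Per Protocol definition and in Protocol 11.1, using the same words in both:

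- For PP membership, limit the treatment, medication and supplement criteria to the pre-baseline windows already stated plus the double-blind phase through the Week 6 HAM-D17.
- Word the treatment criterion as *treatments other than the randomized treatment during the double-blind phase*.
- Add: *Events after the Week 6 HAM-D17 assessment do not affect PP membership.*

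This changes text only. It needs no new data and no change to study conduct, and it leaves the sample size calculation as it stands.

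Separately, the passages on antidepressant use in the last three open-label weeks (Protocol 7.1; SAP, Follow-up Visits) contradict the lists that exclude antidepressants for the whole study (Protocol 5.8; SAP, Per Protocol). Those passages must be reconciled; this point does not depend on how.
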